#### 6.5.4 Other Interventions

Any unplanned diagnostic, therapeutic, or surgical procedure performed from screening through the End-of-Study visit or Extended follow-up visits (for patients in Cohort 4 with a 60 mg/kg dose) must be recorded in the concomitant procedure section in the eCRF, including the date, indication and description of the procedure(s) and outcome.

Any other special considerations, e.g., concerning food, caffeine and physical exercise, should be noted.

## 6.6

### Dose Selection and Modification

This is an open-label study in which participants will receive a single treatment dose of the new L-PZQ ODT (Treatment group 1a, Cohorts 2, 3, and 4) or the commercial PZQ formulation (Treatment group 1b) at Day 1. Therefore, no dose modification is applicable.

If the participant vomits or spits the L-PZQ/Biltricide after dosing, he/she will not receive a new dose of L-PZQ/Biltricide. If vomiting occurs, water and/or food may be given at the Investigator's discretion and this will be documented in the CRF. Subjects will not be excluded from the analysis.

An IDMC will evaluate the interim safety and efficacy data after 30 participants are enrolled and treated in Cohort 4. The data will be summarized and evaluated to decide whether there is a need to increase the dose to 60 mg/kg in Cohort 4 (see Section 9.4.4).

## 6.7

### Treatment Intervention after the End of the Study

Participants who were positive for *S. mansoni* or *S. haematobium* but were not enrolled in the study, or enrolled patients who were not found to be cured at the End-of-Study visit, may be offered treatment with the locally available PZQ 600 mg tablets based on national recommendations.

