#### 4.4 End of Study Definition

A participant has completed the study if he/she has completed all study parts, including stool (Cohorts 1, 2, and 3) or urine (Cohort 4) sampling at the scheduled follow-up visits.

The end of the study is defined as the date of the End-of-study visit (or Extended Follow-up visit urine collection at Week 5 for Cohort 4) of the last participant.

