### **6.5.1 Rescue Medicine**

Biltricide may be administered to address ineffective Schistosomiasis treatment. Other rescue medications may be administered to treat anticipated adverse reactions or anticipated emergency reactions.

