### **6.5.3 Prohibited Medicines**

As referred to in the exclusion criteria (Section 5.2), administration of PZQ or use of any investigational device within 4 weeks prior to administration of the study intervention (PZQ ODT or Biltricide) and during the entire clinical study is not permitted.

If the administration of a non-permitted concomitant drug becomes necessary during the study, e.g., because of AEs, the participant should be discontinued from the study but only after consultation with the Sponsor. Children who require malaria treatment after receiving study treatment will not be withdrawn from the study, but because some anti-malarial agents (e.g.,

artemisinin derivatives) have activity against *Schistosoma* spp. (Liu et al, 2011), they will be excluded from the primary efficacy analysis.

For children being breastfed, administration of PZQ to nursing mothers is not allowed in the 3 days prior to PZQ ODT administration (see Section 6.5).

The concomitant administration of agents that induce the drug-metabolising enzyme system in the liver (cytochrome P450), such as certain antiepileptics (e.g., carbamazepine or phenytoin), glucocorticosteroids (e.g., dexamethasone) or chloroquine, may lead to reduced plasma levels of PZQ and will not be allowed. The concomitant administration of rifampicin, which is a strong inducer of cytochrome P450, or of other cytochrome P450 inducers, is contraindicated as no therapeutically effective plasma levels of PZQ can be expected in that setting.

Similarly, the concomitant administration of agents that inhibit the cytochrome P450 system, e.g., cimetidine, may lead to increased plasma levels and a prolonged retention period of PZQ and will not be allowed.

As consumption of grapefruit may lead to increased PZQ levels, grapefruits and grapefruit juice products will not be allowed during confinement. In case a participant may have been enrolled and dosed after grapefruit consumption, a protocol deviation will be issued, however participants will not be discontinued from the study and data won't be excluded from the analysis. The Investigator will need to enquire the eventual consumption of grapefruit in the 24 hours before enrolment and ensure that the child eats only the standard meals during confinement. At discharge, he will explain the parent/guardian/legally authorized representative the importance of abstaining from grapefruit consumption until 24 hours after the study intervention administration.

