### 7.2 Participant Discontinuation/Withdrawal from the Study

This is a single-dose treatment study. If a participant withdraws prior to administration of the study treatment, the End-of-Study visit will be performed and no attempts will be made to collect additional data. No further evaluations will be performed, except for safety purpose when applicable.

- A participant may withdraw from the study at any time, upon request of participant's parent or guardian/legally authorized representative (i.e., withdrawal of consent) or if the child communicates (verbally or opposing resistance) that he/she is unwilling to continue, and without giving a reason. However, the reason should be obtained when it is possible to do so, and then the reason should be reported in the appropriate Case Report Form.
- The participant may be withdrawn by the Investigator due to participation in another clinical study.
- The participant may be withdrawn at any time at the discretion of the Investigator for safety, behavioral, compliance, or administrative reasons.
- The participant may be withdrawn if lost to follow-up.
- If a participant withdraws from the study, no further evaluations should be performed, and no attempts should be made to collect additional data, with the exception of safety data, which should still be collected if possible, but not captured in the database.
- If a participant is withdrawn from the study because of a treatment-limiting AE, thorough efforts should be made to clearly document the outcome.
- Data obtained prior to a participant's withdrawal will still be included in the efficacy and safety analysis.
- Participants withdrawn from the study will not be replaced.

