#### 9.4.1 Efficacy Analyses

The primary efficacy analysis will be performed on the mITT population of Cohort 1. The primary endpoint of cure rate will be calculated as the percentage of egg-positive participants at baseline who become egg-negative after treatment (as assessed by the Kato-Katz method). The exact 95% CI will be calculated based on the Clopper-Pearson method. Cohorts 2, 3, and 4 will be analyzed similarly.

The secondary endpoint of cure rate by POC-CCA® (Cohorts 1, 2, and 3) will be analyzed in the same manner as the primary endpoint, with proportion cured and its 95% CI.

The secondary endpoint of ERR will be analyzed for each of the cohorts and treatment group (Cohort 1) as group-based ERR (arithmetic and geometric) and as individual ERR (arithmetic and geometric).

Subgroup analyses will also be conducted by severity of infection (light vs. moderate/heavy infection stratification factor), country and gender. In Cohort 4, subgroup analyses will also be done by specific age groups (e.g., 3 months to 24 months of age, 2 to < 4 years of age, 4 to 6 years of age).

Sensitivity analyses may be performed on the ITT population of Cohort 1, to determine the impact of participants requiring malaria treatment, and on the PP population of Cohort 1, to assess the impact of any protocol deviations (such as completing study assessments outside the Day 17 to 21 window).

Analysis of Cohort 3 will be a pooled analysis, including the mITT population from this study and the mITT population for participants 3 to 24 months of age in the Phase II study MS200661-0005 (Cohorts 8 and 9). A logistic regression model with adjustment for study and site variability will be used to estimate cure rate.

Analysis of Cohort 4 will be performed only on the mITT population and using the same methods as for Cohort 1.

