| Primary (mITT) | 
At each assessment visit after treatment, clinical cure is defined as no parasite eggs in the urine samples.
 
Egg counts will be determined by urine examination using the urine filtration technique: The first sample will be collected during the pre screening period (Day -28 to Day -1) and the second and the third one within a maximum of 5 days thereafter as baseline. At the End-of-Study visit (between Day 17 and 21) Cohort 4 participants will be asked to provide three urine samples (about 10 mL each): the first one will be collected within the 17 to 21-day window and the other two within a maximum of 5 days following collection of the 1st sample, for analysis by the filtration method.
 
Similarly, at the Extended Follow-up
 | 
No hypothesis testing will be performed. Point estimates and corresponding two-sided 95% CIs will be determined.
 
Subjects cured of infection during the trial will be labelled as "responders". At each of the End of Study visit (17 to 21 days after treatment, according to the eCRF page "End of Study (Day 17 to Day 21)") and the Extended Follow-up visit (35 to 40 days after treatment, according to the eCRF page "Extended Follow-up (Day 35 to Day 40)"), responders will be defined as subjects with no parasite eggs urine samples, (as determined by urine filtration method)
 
Responders and non-responders will be coded as follows:
 
 For responders, response = 1 For non-responders, response = 0 
The proportion of responders in each cohort will be determined based on a binomial distribution. Exact 95% CIs will be calculated based on the Clopper-Pearson method. The PROC FREQ procedure in SAS will be used with the appropriate BINOMIAL and EXACT statements for point estimates and corresponding 95% CIs.
 
Point estimates and corresponding 95% CIs will be presented for cure rate, in terms of proportion of responders, by cohort. Response will be listed by cohort and subject. Estimates of cure rate will be presented graphically in the form of forest plots presenting point estimates and 95% CIs.
 
Results will be presented for each analysis set.
 | 
If the End of Study or Extended Follow-up visit egg count is missing, carried forward for imputation. According to this rule subjects with missing egg count data at post-treatment assessment will be considered as non-responders at the End-of-study visit. For cohort 4b, if the assessment at Extended Follow-up visit is missing, the assessment result at End-of-study visit will be carried forward.
 |

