| 
Primary (PP)
 | | | 
No Imputation will be done.
 |

| | | | |
|--|---|---|--|
| | | 
Point and interval estimates of ERR_A, ERR_G and proportion of individuals with $iERR \geq 90\%$ will be presented by treatment group. 95% CIs of these 3 parameters will be calculated by bootstrapping (using SAS procedure SURVEYSELECT). Mean Kato-Katz egg counts will be listed by cohort and subject and time point. Estimates of ERR_A, ERR_G and $iERR$ will be presented graphically in the form of boxplots, by cohort.
 
Results will be presented for each analysis set.
 | |
| Secondary endpoint: Egg Reduction Rate (ERR) in children 2 to 3 years of age and in infants and toddlers 3 months to < 24 months of age infected with S. mansoni (Cohorts 2 and 3, respectively) and in children 3 months to 6 years of age infected with S. haematobium (Cohort 4). | | | |
| Primary (mITT) See 14.1.2 for details about analysis for participant 3 to 24 months of age (Cohort 3). | ERR from pre treatment to 17 to 21 days after treatment, using parasite egg counts as determined by the Kato-Katz method for Cohorts 2 and 3 and the urine filtration method for Cohort 4. Additionally, for Cohort 4b participants ERR from baseline to 35 to 40 days after treatment, using parasite egg counts as determined by the urine filtration method, | Same as Cohort 1 (Secondary analysis). | 
If the End of Study egg count is missing, it will be imputed using the Last Observation Carried Forward (LOCF) approach. Subjects with all post-baseline egg counts missing will be considered non-responders.
 
For cohort 4b, if egg counts is missing only at Extended Follow-up visit, it will be imputed by taking the value from End-of-study visit.
 |
| Secondary endpoint: cure rate as demonstrated with use of the commercially available point-of-care circulating cathodic antigen (POC-CCA®) test (Cohorts 1, 2, and 3). | | | |

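### Cohort 4b at Day 35–40: the protocol is unclear on praziquantel after failure at Day 17–21, and no mITT rule stops a re-treated, sampled, egg-free child from counting as an L-PZQ cure

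*Protocol*

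**What the plan says.** **Praziquantel after failure**
- Protocol 6.7 says that "enrolled patients who were not found to be cured at the End-of-Study visit, may be offered treatment with the locally available PZQ". The Schedule of Activities puts the End-of-Study visit at Day 17–21. The section's heading refers to the period after the end of the study.
- Protocol 6.5.1 says "Biltricide may be administered to address ineffective Schistosomiasis treatment" and names no visit.
- Protocol 6.5.3 says that giving praziquantel before dosing (within 4 weeks) "and during the entire clinical study is not permitted". It adds that a child who needs a non-permitted drug should be discontinued, after consultation with the Sponsor.
- Protocol 7.2: "If a participant withdraws from the study, no further evaluations should be performed", safety data excepted.
- Protocol 4.4 sets the end of the study at the End-of-Study visit or the "Extended Follow-up visit urine collection at Week 5 for Cohort 4".

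**Analysis of Cohort 4**
- Malaria treatment is the only treatment received after enrolment that removes a child from mITT (protocol 9.3, SAP 8.2).
- Protocol 9.4.1: "Analysis of Cohort 4 will be performed only on the mITT population". The Cohort 4 cure-rate row of SAP 14.2 lists only mITT, but also says that results will be shown for each analysis set. SAP 8.2 defines a PP set for 4b that requires two post-baseline measurements.
- At each of the two visits, "responders will be defined as subjects with no parasite eggs urine samples" (SAP 14.2).
- On missing data: "For cohort 4b, if egg counts is missing only at Extended Follow-up visit, it will be imputed by taking the value from End-of-study visit" (SAP 14.2, ERR). The cure-rate row has the same rule.

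**Recording of medication**
- Protocol 6.5 and SAP 12 cover the whole study. Protocol 6.5.3 and 8.2.5 stop at the End-of-Study visit. Protocol 6.5.4 already extends the recording of procedures to the Extended Follow-up visit for the 60 mg/kg group.

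**The concern.** For every group except 4b, the End-of-Study visit is the last efficacy assessment, so treating failures after it cannot disturb the results. Version 1.2 of the protocol added the Day 35–40 assessment, but 6.7 still ties the offer of praziquantel to the Day 17–21 visit. A site could read it as permission to treat a 4b failure two to three weeks before that child's last efficacy sample.

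If that happens and the child is still sampled, the Day 35–40 result reflects L-PZQ plus a second course of praziquantel, yet it is reported as the effect of L-PZQ alone. In the mITT analysis the error can only move the cure rate and ERR upward.

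Day 35–40 cure rate and ERR are named secondary endpoints. They also belong to the interim analysis of the first 30 children at 60 mg/kg, which is meant to inform whether another *S. haematobium* trial is needed (protocol 9.4.4).

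**Working it through.** **1. What happens to a 4b child who fails at Day 17–21 and is then given praziquantel**

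| Route | Day 35–40 value | Imputed mITT | mITT without imputation |
|---|---|---|---|
| Discontinued, not sampled (6.5.3, 7.2) | missing | Day 17–21 failure carried forward; no inflation | cure: child stays in the denominator (SAP 9); ERR: child drops out of the post-treatment mean |
| Kept in the study, sampled, egg-free | observed, zero eggs | counts as cured; zero enters the ERR | the same |

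The second row is the gap. Membership of mITT, the cure definition and the carry-forward rule are all silent on re-treatment, and carry-forward needs a missing value. The SAP 9 denominator rule concerns proportions, so it does not protect the ERR in the first row.

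**2. The plan's own precision figure.** Protocol 9.2 expects 60 × 0.95 = 57 mITT children and, at a 75% cure rate, a precision of 13.2%. The exact (Clopper-Pearson) 95% interval for 43/57 = 75.4% is 62.2 to 85.9. The distance to the lower limit is 13.2 points, so the figure reproduces. The distance to the upper limit is 10.4 points.

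**3. Size at the final analysis.** Assume 43/57 cured at Day 17–21, 14 failures, and no other change by Day 35–40. Let k be the number of re-treated failures who are sampled and egg-free. The apparent rate is (43 + k)/57, and each child adds 1/57 = 1.75 points.

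| k | Apparent cure rate | Exact 95% CI |
|---|---|---|
| 0 | 43/57 = 75.4% | 62.2–85.9 |
| 2 | 45/57 = 78.9% | 66.1–88.6 |
| 6 | 49/57 = 86.0% | 74.2–93.7 |
| 7 | 50/57 = 87.7% | 76.3–94.9 |
| 12 | 55/57 = 96.5% | 87.9–99.6 |

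Six such children add 10.5 points, more than the upper distance of 10.4. Seven are the fewest for which the interval excludes 75.4%.

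**4. Size at the 60 mg/kg interim.** 30 × 0.95 is about 28 mITT children. With 21/28 = 75.0% (55.1–89.3), each such child adds 1/28 = 3.6 points. Five give 26/28 = 92.9% (76.5–99.1), the first interval that excludes 75.0%.

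**5. ERR.** Let e be the arithmetic ERR without re-treatment and s the share of failures who are re-treated and cleared. If they are average among failures, the apparent ERR is 1 − (1 − e)(1 − s). With e assumed at 90%, s = 0.125 gives 1 − 0.10 × 0.875 = 91.25%, and s = 0.90 gives 1 − 0.10 × 0.10 = 99.0%.

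In the table without imputation, suppose instead that 7 of the 14 failures are discontinued and unsampled, are average among failures, and the pre-treatment mean still uses all 57. The post-treatment mean becomes 0.10 × 0.5 × 57/50 = 0.057 of the pre-treatment mean, an apparent ERR of 94.3%.

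**The case against.** **The heading of 6.7.** Read with its heading and with 4.4, 6.7 can mean that the End-of-Study result decides who is offered praziquantel, and the heading decides when: for 4b, after Week 5. That agrees with 6.5.3. The reading is fair, and it is why the text is ambiguous and only partly contradictory. A reader might infer that the protocol plainly directs re-treatment before Day 35–40; the documents do not support that. But the body of 6.7 names only the Day 17–21 visit, and 6.5.1 has no timing at all, so a site could act on either reading.

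**The discontinuation route.** Under 6.5.3 and 7.2 a re-treated child should leave the study and not be sampled, and the failure is then carried forward. This stands for the imputed table. It is not a complete safeguard: discontinuation is worded as something that should follow Sponsor consultation, and 6.7 does not mention it.

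**Per protocol.** The SAP defines a PP set for 4b, treats praziquantel as a prohibited medication (Appendix B), and promises results by analysis set. It would be wrong to infer that no PP result is planned, although protocol 9.4.1 limits Cohort 4 to mITT. PP is still not a remedy. It removes a known failure instead of scoring one, and only if the dose is recorded, on which the protocol sections differ. The SAP's listings of prohibited medication depend on the same record.

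**Weight.** The endpoint is descriptive, Cohort 4 is not meant as independent proof of efficacy, and the interim triggers no action in this study. All true, and it limits the importance of the point.

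**Conclusion.** The point holds in a limited form. On one permitted reading of the protocol, a 4b child who fails at Day 17–21 can be given praziquantel, stay in the study and be sampled at Day 35–40. No mITT, cure or imputation rule then prevents an egg-free result from counting as an L-PZQ cure, or the post-rescue count from entering the ERR. A smaller gap affects the ERR without imputation, where a discontinued failure drops out of the post-treatment mean.

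The documents do not give the number re-treated. The effect is zero if there are none, and otherwise 1.75 points per such child at 57, or 3.6 points at about 28. A reader might take 87.7% or 96.5% as a forecast. They are illustrations: they assume the planned 75% cure rate, no other change between visits, and children kept and sampled despite 6.5.3 and 7.2.

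The primary endpoint is unaffected. So are the Day 17–21 mITT results, provided any praziquantel is given after that visit's samples are complete. The matter is worth fixing because the possible mITT bias runs one way, reaches an analysis that informs a further trial, and costs little to close.

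**What to change.** 1. **SAP 14.2, scoring rule.** For a 4b child given praziquantel after the End-of-Study assessment and before the last Day 35–40 sample, do not use Day 35–40 samples taken after that dose.
   - In the imputed mITT tables and at the 60 mg/kg interim, carry the End-of-Study result forward for both cure and ERR, as for missing data.
   - In the tables without imputation, treat the Day 35–40 value as missing, show the number of such children, keep them in the cure-rate denominator as SAP 9 states, and compute the ERR on children with both values. That ERR still omits known failures, so it should be read beside the imputed one.
2. **Recording.** Align protocol 6.5.3 and 8.2.5 with 6.5 and SAP 12, so that concomitant medication is recorded through the Extended Follow-up visit for 4b, as 6.5.4 already does for procedures.
3. **Protocol text.** Reconcile 4.4, 6.5.1, 6.5.3, 6.7 and 7.2 on praziquantel between the two visits. Which clinical rule applies is for the sponsor and investigators; this review takes no position.

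The cost is one SAP rule and a protocol and eCRF clarification. No extra children or visits are needed. The reported Day 35–40 cure rate and ERR may be lower.

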## 6.8

### Special Precautions

The medication administration part of the study will be conducted in a setting with access to basic emergency facilities. Equipment and other agents (epinephrine, prednisolone equivalents, etc.) will be made available at the study site in case of severe allergic reactions.

Participants will be observed when receiving the study intervention. They will remain in the facility for at least 12 hours after dosing and will be closely monitored.

## 6.9

### Management of Adverse Events of Interest

No clinically significant risk is anticipated to participants at the tested dose. Participants will remain in the facility for at least 12 hours after dosing and will be closely observed. A participant may be confined for up to 24 hours in the event of any AE requiring prolonged observation. Based on the PK properties of PZQ, drug-related AEs (mentioned in Section 8.2) are expected to occur within approximately 12 hours after dosing. In the event that a participant stays in the clinic due to reasons other than an AE or serious adverse event (SAE), the discharge time will be in line with at least 12 hours and the additional stay will not be reported as an AE. In addition, follow-up of AEs will be performed, if required, during the first week after dosing (see Section 1.3, Schedule of Activities) but not necessarily in the facility.

 An Independent Data Monitoring Committee (IDMC) meeting was held on the 09 March 2020 and a decision was made to increase the dose in Cohort 4 to 60 mg/kg.

AEs will be managed in the participating health facility by study medical doctors who will remain in the facility during the study.

